This is a single center, randomized; singe blinded, two-arm trial comparing the effects of direct placement of LPT over the spared neurovascular bundles vs. standard care (no placement of tissue) on erectile recovery and quality of life in patients undergoing bilateral nerve sparing radical prostatectomy for prostate cancer.

VCUT for Erectile Recovery During Bilateral Nerve Sparing RRP Protocol												
	Consult	Baseline Eval	Surgical Day	Post Op Day 1	2 weeks Post Op	1 Month Post Op	3 months Post Op	6 months Post Op	9 months Po	12 months Post Op	18 Months Post Op	
Informed Consent	x											
Medical Clearance		x										
IIEF	x				x	x	x	x	x	x	x	
SEQ	x				x	x	x	x	x	x	x	
EPIC, SF12, AUA SI	x				x	x	x	x	x	x	x	
Randomization	x											
Rx (PDE5i)					x							
AE Monitoring		x	x	x	x	x	x	x	x	x	x	
PSA Monitoring						x						

The sample size will be 10 patients randomized to each study arm (20 patients total). Study procedures will involve screening and informed consent after initial consultation, baseline evaluation including medical clearance and completion of validated questionnaires, and randomization.

In order to minimize the need for research-only in-person visits, telemedicine visits may be substituted for in person clinical trial visits or portions of clinical trial visits where determined to be appropriate and where determined by the investigator not to increase the participant's risks. Prior to initiating telemedicine for study visits the study team will explain to the participant, what a telemedicine visit entails and confirm that the study participant is in agreement and able to proceed with this method. Telemedicine acknowledgement will be obtained in accordance with the Guidance for Use of Telemedicine in Research. In the event telemedicine is not deemed feasible, the study visit will proceed as an in-person visit. Telemedicine visits will be conducted using HIPAA compliant method approved by the Health System and within licensing restrictions

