The primary outcome variable is the patient's score on the IIEF questionnaire (erectile function domain) at 1,3, 6, 9, 12 and 18 months post-surgery. Comparison of changes in initial IIEF score will be evaluated to determine treatment efficacy. We anticipate a gradual increase in baseline IIEF score over the course of the study. The secondary outcome variables will be the patient's scores on the QEQ, combined EPIC/SF-12/AUASI questionnaires, other domains of the IIEF questionnaire. For statistical analysis based on ANOVA, the sample size is powered for a power of 80% with one-sided alpha of 0.05 showing a sample size of 23 patients in each arm is necessary to detect an expected difference of 5 points in IIEF scores (i.e. 20 vs. 15) at 6 months post-surgery. Therefore, the study is planned to enroll 30 patients in each arm. This sample size will accommodate dropout rate during follow-up.

6. Risks

Completion of the questionnaires and administration of Stravix are the only 2 procedures from this protocol that are outside of the realm of standard of care for the radical prostatectomy patient. All of the participants will be exposed to the questionnaires pre operatively and can assess whether they are willing to complete the trial, which will include 6 additional administrations of the questionnaires. If the questionnaires cause any type of discomfort or uneasiness at that time or any time during the study, the participant can decide to end their involvement with the protocol.

There are no contraindications to the use of Stravix. Smith and Nephew (Columbia, MD) reports that the product has been directly applied to spared neurovascular bundles in approximately 250 radical prostatectomies. Tissue donor screening methods are limited; therefore, certain diseases may not be detected.

The following complications of tissue transplantation may occur:⁵

- Transmission of diseases of unknown etiology;
- Transmission of known infectious agents including, but not limited to, viruses, bacteria, and fungi;
- Immune rejection of implanted Stravix®; or
- Loss of function and/or integrity of Stravix® due to resorption, fragmentation, and/or disintegration.

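### Efficacy is judged on change from the pre-surgical IIEF score with no baseline covariate; adjusting for that score would be a cheap, modest gain at 23 to 30 per arm

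*Combined protocol and SAP*

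**What the plan says.** Section 5 (Study Statistics) describes the primary outcome as the patient's "score on the IIEF questionnaire (erectile function domain) at 1,3, 6, 9, 12 and 18 months post-surgery". It then says how efficacy will be judged: "Comparison of changes in initial IIEF score will be evaluated to determine treatment efficacy". The only method named is in the sample-size sentence, "For statistical analysis based on ANOVA", which does not say whether a one-way or repeated-measures analysis is meant. That sentence sizes the trial at 23 per arm (80% power, one-sided 0.05) to detect "an expected difference of 5 points in IIEF scores (i.e. 20 vs. 15) at 6 months post-surgery", and "the study is planned to enroll 30 patients in each arm" follows from it. No covariate is named in any section.

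The pre-surgical score is available. Section 2 (Study Procedures) lists "baseline evaluation including medical clearance and completion of validated questionnaires, and randomization", and its schedule marks the IIEF at the consult. Section 3 admits only men with an IIEF-5/SHIM score of 18 or more.

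Two other statements bear on the point. Section 2 gives a different size: "The sample size will be 10 patients randomized to each study arm (20 patients total)". Section 5 also says "We anticipate a gradual increase in baseline IIEF score over the course of the study". A baseline cannot increase, so this presumably means expected recovery after surgery; the point is one of wording only.

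**The concern.** Analysing change subtracts the whole baseline score, which amounts to assuming that a 1-point higher pre-surgical score predicts a 1-point higher post-surgical score. Here the baseline is taken before an operation that can itself cause erectile dysfunction, in men selected for good function, so the slope could be well below 1. If it is, subtracting the baseline adds noise and carries chance baseline imbalance into the estimate. Estimating the slope from the data avoids having to guess it.

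Section 5 also moves between a score, a change and a 6-month score difference. With the baseline score in the model, the score and change analyses give the same arm difference, so that ambiguity stops mattering. At stake are some power and some protection against chance imbalance, not validity: under randomization both analyses target the same 5-point difference without bias.

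**Working it through.** **Inputs from the documents.** Difference of 5 points, one-sided 0.05, 80% power, 23 evaluable and 30 enrolled per arm (section 5); 10 per arm (section 2).

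**Inputs that are assumed.** The documents give no SD and no correlation.
- 6-month SD (sf): the stated 23 per arm cannot be reproduced without an SD, so it was solved backwards. A t-test with 44 df has 80% power at n = 23 when sf = 6.7135.
- Baseline SD (sb) and baseline-to-6-month correlation (ρ): main grid sb 2-3, ρ 0.1-0.3. The SHIM floor suggests a narrow baseline, but SHIM is not the domain score, so a wide grid (sb 2-5, ρ 0-0.7) was also run.

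**Formulas** (n per arm, noncentral-t power)
- Unadjusted score: variance sf², df 2n−2
- Change: variance sf² + sb² − 2ρ·sf·sb, df 2n−2
- Adjusted: variance sf²(1−ρ²)(1 + 1/(2n−4)), df 2n−3
- Slope of 6-month score on baseline: ρ·sf/sb

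**Example**, n = 23, sb = 3, ρ = 0.1. Change: 45.07 + 9 − 4.03 = 50.04, power 0.763. Adjusted: 45.07 × 0.99 × (1 + 1/42) = 45.68, power 0.795.

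**Main grid, power for change / adjusted**

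| sb, ρ | slope | n = 10 | n = 23 | n = 30 |
|---|---|---|---|---|
| 2, 0.1 | 0.34 | 0.474 / 0.466 | 0.790 / 0.795 | 0.878 / 0.884 |
| 2, 0.3 | 1.01 | 0.514 / 0.492 | 0.832 / 0.824 | 0.910 / 0.906 |
| 3, 0.1 | 0.22 | 0.451 / 0.466 | 0.763 / 0.795 | 0.856 / 0.884 |
| 3, 0.3 | 0.67 | 0.506 / 0.492 | 0.824 / 0.824 | 0.905 / 0.906 |
| Unadjusted score | – | 0.483 | 0.800 | 0.886 |

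Simulation (40,000 trials per scenario) agrees: at n = 23, sb 3, ρ 0.1, 0.764 for change and 0.796 for adjusted.

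**Wide grid, change minus adjusted, in points of power.** −15.5 to +0.8 at 23 per arm; −14.2 to +0.4 at 30; −10.3 to +2.4 at 10. The double-digit losses need sb 4-5 with low correlation. A steep slope also hurts change: with sb 2 and ρ 0.7 (slope 0.7 × 6.71/2 = 2.35) it loses 4.6 points at 23 per arm and 7.9 at 10.

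**Where change is better.** At 23 per arm, only for slopes of 0.48-1.47 (sb 2), 0.67-1.29 (sb 3) or 0.84-1.12 (sb 5), and by at most 0.8 points.

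**If the unadjusted score was meant.** Main grid, adjusted minus score: −0.5 to +2.4 points at 23 per arm, −0.2 to +2.0 at 30, −1.7 to +0.9 at 10. The worst case for adjusting is ρ = 0: 0.792 against 0.800 at 23, 0.881 against 0.886 at 30, 0.463 against 0.483 at 10.

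**If 6.71 is instead the SD of change.** The adjusted residual variance cannot exceed that of change, so adjusted power is at least 0.792 at 23 and 0.881 at 30.

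**Chance imbalance.** A one-SE baseline difference is sb·√(2/n), and change carries |1 − slope| of it into the estimate. Main grid, in IIEF points:

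| n per arm | Shift in change estimate | Slope-estimation error, adjusted |
|---|---|---|
| 30 | 0.0-0.6 | about 0.2 |
| 23 | 0.0-0.7 | about 0.3 |
| 10 | 0.0-1.0 | about 0.7 |

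For scale, the SE of the treatment difference at 30 per arm is 6.71 × √(2/30) = 1.73.

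**The case against.** The strongest case against is that this is a preference between two unbiased analyses and that its size rests on inputs the documents do not give. On the main grid, three of the four scenarios differ by less than 1 point of power at both 23 and 30 per arm; the loss of about 3 points is one scenario (sb 3, ρ 0.1). The double-digit losses need a baseline more variable than the entry rule suggests. The absence of a covariate is read from silence in a one-paragraph statistics section. If the score and not the change is to be analysed, the comparison with change does not apply, and the more basic gap is that section 5 does not settle which is meant. If the trial runs at 10 per arm, the benefit largely disappears.

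Most of this stands as a limit on size. It does not remove the point. At 23 to 30 per arm the possible loss from adjusting is bounded at about 0.8 points whether change or score was intended, while the possible loss from not adjusting is several times that. The covariate also makes the choice between score and change immaterial to the arm difference. The objection about 10 per arm is correct: on the main grid change is ahead in three of four scenarios. That near-neutrality does not extend to the wide grid, where change can lose up to 10.3 points at 10 per arm.

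**Conclusion.** The point holds as a modest improvement worth making, with medium confidence. It is not a validity error. At section 5's 23 to 30 per arm, change ranges from about 3 points of power worse than the adjusted analysis to under 1 point better on the main grid, and the robustness gain is small against an SE of about 1.7 points. These figures depend on the back-solved SD of 6.71 and the assumed baseline SD and correlation; if the true slope is near 1, change is near-optimal and the gain vanishes. At 10 per arm there is no clear advantage either way on the main grid. The point does not resolve the conflict between 10 and 30 per arm.

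**What to change.** In section 5, prespecify that the post-surgical IIEF erectile function domain score is compared between arms with the pre-surgical domain score (not the SHIM entry score) as a covariate. Use ANCOVA at 6 months, the only visit for which the sample size is justified, or a repeated-measures model over the listed visits with the same covariate and a 6-month contrast. If change is to be reported, put the same covariate in the change model, which gives the identical arm difference. If the trial runs at 10 per arm, either analysis is defensible on the main-grid figures; state one in advance. Reword the sentence about an increasing baseline as expected recovery after surgery.

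The cost is a few words in section 5 and one degree of freedom, with no new data or visits. The largest power loss from adjusting is about 0.8 points at 23 per arm, 0.5 at 30 and about 2 at 10.

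### The plan names ANOVA but claims 80% power for a one-sided 0.05 test; on that claim, an ordinary two-arm F-test at 0.05 has about 70% power at 23 per arm

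*Combined protocol and SAP*

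**What the plan says.** Section 5 names the method and the error rate in one sentence: "For statistical analysis based on ANOVA, the sample size is powered for a power of 80% with one-sided alpha of 0.05". The same sentence says that "a sample size of 23 patients in each arm is necessary". The target effect is a 5-point gap on the IIEF (20 against 15), judged six months after the operation. The plan then adds, to allow for dropout at a rate it does not give: "Therefore, the study is planned to enroll 30 patients in each arm".

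Section 2 (Study Procedures) gives a different size: "The sample size will be 10 patients randomized to each study arm (20 patients total".

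The plan gives no SD, no directional contrast or one-sided t-test, and no separate significance level for an ANOVA F-test. It does not say whether the ANOVA is a comparison at 6 months, an analysis of change, or a repeated-measures model over the six post-surgery visits.

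**The concern.** In a two-arm comparison the ANOVA F-statistic is the square of the t-statistic. A large F arises from a difference in either direction, so the F-test at 0.05 is the same test as a two-sided t-test at 0.05. The power in Section 5 is tied to a one-sided 0.05 level. The quoted power and the usual form of the named analysis therefore do not belong together.

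If the F-test is run at 0.05, the chance of missing the targeted 5 points with 23 evaluable patients per arm is about 30%, where the plan implies 20%. Most of the margin between 23 and 30, which the plan sets aside for dropout, is then used up by the change of test. One-sided testing can be defended in an early trial and is not itself the complaint.

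**Working it through.** **Inputs.** From Section 5: difference 5 points, 23 per arm needed, one-sided alpha 0.05, power 80%, 30 per arm planned. From Section 2: 10 per arm. The SD is not given and is back-solved as an assumption.

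**1. Can the plan's 23 be reproduced?** Not forwards, because there is no SD. Backwards, by the normal approximation, SD = 5 × √(23/2) / (z for alpha + z for power):
- One-sided 0.05: 5 × 3.391 / (1.645 + 0.842) = 6.82. With the exact noncentral t on 44 df, 80% power at 23 per arm needs SD 6.71. The SDs for which 23 is the exact answer run from 6.56 to 6.71.
- Two-sided 0.05: 5 × 3.391 / (1.960 + 0.842) = 6.05, or 5.92 exactly. For example, SD 6 gives n = 2 × 36 × (2.802)² / 25 = 22.6, which rounds up to 23.

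So 23 per arm is consistent with either sidedness, at different SDs.

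**2. Power of the F-test, taking the stated one-sided 80% at face value.** This needs no SD under the normal approximation. Power of 80% at one-sided 0.05 fixes the standardised difference at 1.645 + 0.842 = 2.486 (from unrounded values). Against the two-sided critical value 1.960, power is Φ(2.486 − 1.960) = Φ(0.526), about 70.1%.

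The exact version uses the noncentral F with 1 and 2n − 2 df and noncentrality λ = (5/SD)² × n/2. For n = 23 and SD 6.71, λ is about 6.38 and power at 0.05 is 69.5%. The same F-test at 0.10 gives 80.0%, which shows that sidedness accounts for the whole gap.

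**3. Power at the sizes that matter (SD 6.71).**

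| Evaluable per arm | One-sided t at 0.05 | F-test at 0.05 |
|---|---|---|
| 10 (Section 2) | 48.3% | 35.1% |
| 23 (Section 5, needed) | 80.0% | 69.5% |
| 29 | 87.6% | 79.6% |
| 30 (Section 5, planned) | 88.6% | 81.0% |

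Over SD 6.56 to 6.82, F-test power is 71.5% to 68.2% at 23 per arm, 82.7% to 79.7% at 30, and 36.5% to 34.2% at 10. Over the same range, 80% by F-test needs 29 to 31 per arm.

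**4. If the one-sided label is a slip.** With SD 5.92 to 6.0, F-test power at 0.05 is 80.0% to 78.9% at 23 per arm, close to what is stated. At 10 per arm the same formula gives about 43% to 42%.

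**The case against.** The strongest objection is that Section 5 never mentions an F-test or an F-test level. ANOVA is a family of models, and a one-sided contrast between the arms within a two-group ANOVA is a legitimate analysis with exactly the stated 80%. This stands to the extent that the 70% belongs to the usual F-test at 0.05 and not to every analysis the sentence could cover. The plan does not name the directional contrast, however, so the reader cannot tell that it is meant.

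Second, a reader might infer that 23 could only have come from a one-sided calculation, so that the ANOVA is certainly underpowered. The documents do not support that. Without an SD, a two-sided calculation with SD about 5.9 to 6.0 also gives 23, and in that case the F-test has its stated power and only the label is wrong.

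Third, a reader might infer a 10% false-claim rate from halving the F-test p-value. That rate requires claims in both directions, each at one-sided 0.05. The plan proposes no claim of harm. A benefit-only claim at one-sided 0.05 carries a 5% rate, as planned.

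Fourth, reducing the analysis to a two-arm test at 6 months is an assumption, since the plan lists several time points and does not state the model. It is nonetheless the comparison on which the sizing sentence is built.

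Finally, the missing SD and the conflict between 10 and 30 per arm are at least as important as the choice of test. That is fair, and the fix covers them.

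**Conclusion.** The point holds in conditional form. Section 5 pairs ANOVA with a one-sided power figure and does not say which test will decide the result. Taking the stated one-sided 80% at 23 per arm as correct (implied SD about 6.7), and assuming a two-arm F-test at 0.05 on the 6-month score, power is about 70% at 23 evaluable per arm and 81% at 30. The planned 30 then leaves almost no dropout allowance. At an SD near 6.56, one or perhaps two patients per arm could be lost. At 6.71, losing one already brings power to 79.6%.

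If instead the calculation was two-sided with SD about 5.9 to 6.0, the F-test has about 79% to 80% power at 23 and the word to correct is the one-sided label. The plan does not allow a choice between these two readings. On either, the 10 per arm in Section 2 falls well short of 80%: 35% by F-test or 48% one-sided on the first reading, and about 42% to 43% by F-test on the second.

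No sum in the plan is shown to be wrong. The defect is that test, sidedness, SD and sample size are not tied together.

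**What to change.** In Section 5, state the SD and its source, and make the test and the power agree in one of two ways:

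- (a) Name a one-sided 0.05 test of the LPT-minus-control contrast in IIEF erectile function score at 6 months, claiming benefit only. This keeps 80% at 23 evaluable per arm. Adjustment for baseline score is an optional gain in precision and is not part of the match, because the calculation mentions no covariate.
- (b) Keep the F-test at 0.05 and restate power as about 70% at 23 evaluable per arm, 81% at 30 and 35% at 10. These figures assume SD 6.7. If the true input was a two-sided calculation with SD about 5.9 to 6.0, correct the label and quote the power for that SD.

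In either case, reconcile the 10 per arm in Section 2 with the 30 in Section 5, give the assumed dropout rate, and state the power for the size actually used.

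The cost is a few sentences. Neither option needs more patients than the 30 per arm already in Section 5. The downside is that a stated figure becomes less favourable: under (b) if the one-sided calculation stands, and under either option if the trial enrols 10 per arm.

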Assessment tools will consist of the following questionnaires, *which will be administered online using a REDCap site hosted by the Data Informatics Services Core within the Johns Hopkins Biostatistics Center or via mail per patient preference*: IIEF questionnaire, the Quality of Erection Questionnaire (SEQ), and the version of the Expanded Prostate Cancer Index Composite (EPIC) that combines the Short Form Health Survey (SF-12) and AUA Symptom Index (AUA-SI). Standard practice associated with surgery, blood transfusion and postoperative laboratory testing will be performed. Operating room time, estimated blood loss, surgical margin status and length of hospital stay will be recorded. Patients will be prescribed a phosphodiesterase type 5 inhibitor (sildenafil, tadalafil or vardenafil) at 1 month following surgery to be used as conventional "on-demand" therapy. Adverse event monitoring will be performed. PSA monitoring is recommended at 3 and 12 months with the definition for biochemical recurrence set as a PSA of 0.2ng/mL (rising from an undetectable level after surgery).

3. Inclusion/Exclusion Criteria

Inclusion Criteria:

1. Male sex 40 to 70 years of age with localized prostate cancer (clinical stage less than or equal to T2a, Gleason grade less than or equal to 3+4=7, including 4+3=7 (Gleason 8 will be excluded), PSA less than or equal to 20 ng/mL)
2. Scheduled to undergo curative radical prostatectomy applying bilateral nerve-sparing procedure
3. Intact pre-surgical erectile function (International Index of Erectile Function [IIEF]-5 / Sexual Health Inventory for Men (SHIM) score greater than or equal to 18)
4. Willingness to attempt intercourse at least 5 times per month following surgery.
5. Has a sexual partner of at least 6 months with current sexual activity (within the past 4 weeks)

Exclusion criteria:

1. Known penile deformity or a history of Peyronie's disease
2. Pre or postoperative androgen therapy
3. Pre or postoperative radiation therapy
4. History of high or low blood pressure that is not controlled
5. Taking nitrates medications
6. History of heart problems such as angina, heart failure, irregular heartbeats, or myocardial infarction
7. History of drug or alcohol abuse
8. Current smoker has a 20 pack/year history of cigarette smoking
9. History of acute or chronic depression
10. History of liver problems or kidney problems
11. History of retinitis pigmentosa or severe vision loss, including a condition called NAION

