The occurrence of any serious adverse effects will end the patient's participation in the study and halt enrollment in the study to determine the safety of continuing the study. Each and every possible adverse effect of LPT will be investigated and treated individually to minimize the participant's discomfort. The safety of having the individual complete the study will also be assessed on an individual basis. At any time the participant can decide to terminate his participation in the study and no penalty or loss of benefits to which they are entitled.

The risks of radical prostatectomy will apply to both groups. These include but are not limited to bleeding, infection, and injury to surrounding structures. Rare complications include rectal injury requiring fecal diversion and acute blood loss anemia requiring transfusion. An ejaculation is expected. Late complications include urinary incontinence, erectile dysfunction, urethral stricture disease, and bladder neck contracture.

7. Confidentiality

Paper consent forms, enrollment check sheets, and other source or study documentation will be kept in a study binder. This binder will be stored in a locked office available only to the study team. Electronic data will be housed in a secure password protected REDCap database maintained by the Data Informatics Services Core within the Johns Hopkins Biostatistics Center. Only the study team will have access to this secure database. Of note, to maintain the protected health information of patients enrolled in this study, only the study Principal Investigator and primary coordinators will have the ability to export data containing identifying information from this master database. For the purposes of analysis, only de-identified data will be exported.

8. Benefits

The patient's conditions may improve as a result of participation in this study, specifically as related to erectile function and quality of life. However, there is no guarantee of this. The information from this research study may lead to a better treatment in the future for people with prostate cancer. The patients may not benefit from participation in this study. Their conditions may not get better or may become worse while they are in this study.

9. Payment and Remuneration

There will be no payment or remuneration for the participants in this study.

10. Costs

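### Section 5 answers dropout only by enrolling more men and names only an unspecified ANOVA; a mixed model on all visits would be a modest, cheap improvement

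*Combined protocol and SAP*

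**What the plan says.** Section 5 (Study Statistics) is the only statistical text.

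- **Outcome.** The primary outcome is the IIEF score ("erectile function domain) at 1,3, 6, 9, 12 and 18 months post-surgery"). Changes from the initial score are to be compared.
- **Method.** The one method named stands in the sample-size sentence: "For statistical analysis based on ANOVA". Nothing says whether this means one visit at a time or repeated measures.
- **Sample size.** The plan states that "the sample size is powered for a power of 80% with one-sided alpha of 0.05", that "a sample size of 23 patients in each arm is necessary", and that the aim is "to detect an expected difference of 5 points in IIEF scores (i.e. 20 vs. 15) at 6 months post-surgery". No SD is given.
- **Dropout.** Enrolment is raised to 30 per arm, with the remark "This sample size will accommodate dropout rate during follow-up". No rate is given.

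No analysis population, missing-data method or sensitivity analysis is stated.

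Three other places bear on who will have outcome data. Section 6 lets a man leave if the questionnaires make him uneasy. It also says "The occurrence of any serious adverse effects will end the" patient's participation, yet two sentences later the safety of completing the study is to be judged man by man. Section 3 lists "Pre or postoperative radiation therapy", and likewise androgen therapy, among the exclusion criteria.

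**The concern.** The outcome comes from sexual-function questionnaires, and men may leave because of those questionnaires. It is plausible that men who recover poorly are the ones who stop returning them. If LPT works, controls score lower, so one tendency shared by both arms would remove more controls. The remaining controls would then look better than their arm as a whole, and the treatment difference would shrink. If the tendency differs by arm, the difference can move either way. Enrolling more men does not change this, because the extra men are subject to the same selection.

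There is also a loss of information. A man who answers at months 1 and 3 and then leaves says something about his likely month-6 score. A month-6 ANOVA ignores him, and a repeated-measures ANOVA that needs complete records ignores him as well. A likelihood-based mixed model uses what he gave.

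**Working it through.** **Step 1: the plan's own figure.** The inputs from Section 5 are a difference of 5, one-sided alpha 0.05 and power 80%. The SD is missing, so 23 cannot be reproduced directly; it can only be solved for the SD.

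n = 2·SD²·(1.645 + 0.842)² / 5², so SD = 5 / (2.487 × √(2/23)) = 5 / 0.733 = 6.82.

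The exact t calculation gives 6.71. The figure of 23 is therefore consistent with an SD of 6.7 to 6.8 and is not shown to be wrong.

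**Step 2: the dropout allowance.** 1 − 23/30 = 7/30 = 23.3%.

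**Step 3: power by number analysed** (one-sided t-test, SD 6.71).

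- 30 per arm: 88.6%
- 27 per arm: 85.4%
- 23 per arm: 80.0%
- 10 per arm: 48.3%

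If 23.3% are lost at a constant rate over the five intervals after month 1, the share kept per interval is (23/30)^(1/5) = 0.948. Month 6 is two intervals later, so 30 × 0.948² ≈ 27 men per arm are seen then and 23 complete month 18. With random loss, a month-6 comparison thus keeps about 85% power, and one restricted to completers about 80%.

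**Step 4: dropout related to score.** This was simulated with assumed inputs:

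- 30 per arm, true month-6 difference 5, SD 6.71, within-man correlation 0.5 to 0.7, an assumed mean profile, and about 23% lost by month 18;
- the chance of leaving depends on the last observed score, with the same rule in both arms; the log-odds of leaving rise by 0.1 to 0.2 for each point lower.

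All three analyses estimate the month-6 difference. The all-visits analysis is generalised least squares with the covariance treated as known.

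| Analysis | Score-dependent: estimate | Score-dependent: power | Random: estimate | Random: power |
|---|---|---|---|---|
| ANOVA, men seen at month 6 | 4.6–4.9 | 79–83% | 5.0 | 85–86% |
| ANOVA, completers only | 4.4–4.8 | 73–79% | 5.0 | 80–81% |
| Likelihood, all visits | about 5.0 | 85–87% | 5.0 | 88% |

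In a separate run of this set-up at correlation 0.7 or 0.5, the shared rule gave losses of 27–31% in controls against 16–20% with LPT. That imbalance is the source of the shrinkage.

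**Step 5: sensitivity to the dropout rule** (SD 6.8, 19–26% lost by month 18).

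- If leaving depends on how far a man falls below his own arm's mean, equally in both arms, all three analyses give about 5.0.
- If the rule differs by arm, the month-6 ANOVA gives 4.5 to 6.0, completers 3.7 to 7.6, and the likelihood analysis 5.0.

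**The case against.** The strongest reply is that the plan is unspecified rather than wrong. A reader might infer that Section 5 commits the trial to a completer analysis, or that a repeated-measures ANOVA will discard every man with one missed form and leave power far below 80%. The documents do not support either inference. ANOVA appears only in the sample-size sentence, its type is not given, no deletion rule is written, and no rate of missed forms is stated. The trial is sized on month 6, so the natural reading is an ANOVA of all men seen at month 6. On that reading the plan roughly keeps its 80%, and the bias under the shared rule is 0.1 to 0.4 points (5.0 − 4.9 and 5.0 − 4.6), toward no effect. This part of the reply stands and limits the size of the point.

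A reader might also infer that the protocol itself removes men after randomisation. Section 6 is ambiguous: one sentence ends participation after a serious adverse effect, while another leaves completion to individual assessment. Section 3 does not say that men who later receive radiation or androgen therapy are dropped from follow-up or analysis. These are passages to reconcile, not settled rules of loss.

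Two further cautions are fair. Treating the covariance as known flatters the likelihood analysis. That analysis also removes bias only when dropout depends on scores already observed.

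The reply does not remove the main point. Extra enrolment cannot correct outcome-related loss, and in the score-dependent runs the all-visits analysis was closer to 5 points and had more power than either form of ANOVA.

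**Conclusion.** The point holds as a cheap improvement. Against the natural month-6 reading, an all-visits analysis recovers about 0.1 to 0.4 of 5 points and a few percentage points of power (85–87% against 79–83%). Against a completer analysis it recovers 0.2 to 0.6 points, with 85–87% power against 73–79%. With random dropout there is no bias, and the gain is in power alone: 88% against 85–86% or 80–81%.

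These sizes rest on 30 men per arm and on an SD, correlation, mean profile and dropout rule that the documents do not give. They show that bias is possible, not that it will occur. The stated 23 per arm is not shown to be wrong.

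Section 2 gives 10 per arm (20 in total) where Section 5 gives 30. That is a separate conflict and must be reconciled. At 10 per arm there is no dropout allowance, and power at the back-solved SD is about 48% before any loss.

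**What to change.** In Section 5, replace the reference to ANOVA with wording such as this:

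- All randomised men are analysed in the arm to which they were assigned.
- IIEF erectile function at 1, 3, 6, 9, 12 and 18 months is analysed with a mixed model for repeated measures, with terms for arm, visit, arm-by-visit and baseline IIEF erectile function. All available visits are used, including those of men who later stop.
- The primary test is the arm contrast at month 6, the visit used for the sample size.
- One sensitivity analysis shifts imputed scores downward after dropout, because the mixed model cannot deal with dropout that depends on unobserved scores.
- If only 20 men are enrolled, a simple covariance (compound symmetry or AR(1)) is used with a small-sample correction to the degrees of freedom.

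State the assumed SD and dropout rate beside the sample size. Reconcile the two sentences in Section 6 on participation after a serious adverse effect. State how outcome data are handled for men who receive radiation or androgen therapy after randomisation.

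The cost is wording and slightly more programming, with no new patients or data. The one downside is that the covariance must be kept simple in a small sample.
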